5.2.6.2 Adverse event collection and reporting

5.2.6.2.1 AE Collection

The investigator shall maintain and keep detailed records of all AEs in the patient files.

The following must be collected and documented on the appropriate CRF(s) by the investigator:

- From signing the informed consent onwards until the individual patient's end of study: all AEs (serious and non-serious) and all AESIs.
- After the individual patient's end of study: the investigator does not need to actively monitor the patient for new AEs but should only report any occurrence of cancer and trial treatment related SAEs and trial treatment related AESIs of which the investigator may become aware of by any means of communication, e.g. phone call. Those AEs should be reported on the BI SAE form (see [section 5.2.6.2.2](#)), but not on the CRF.

Vital Status Data Collection

Patients who discontinue trial medication prematurely, who agree to be contacted further but do not agree to physical visits, should be followed up as described in [section 3.3.4.1](#), withdrawal from trial treatment. From then on until the individual patient's end of the trial the investigator must report all deaths/fatal AEs regardless of relationship, and trial treatment related SAEs and trial treatment related AESIs the investigator becomes aware of.

5.2.6.2.2 AE reporting to the sponsor and timelines

The investigator must report SAEs, AESIs, and non-serious AEs which are relevant for the reported SAE or AESI, on the BI SAE form via fax immediately (within 24 hours) to the sponsor's unique entry point (country specific contact details will be provided in the ISF). The same timeline applies if follow-up information becomes available. In specific occasions, the investigator could inform the sponsor upfront via telephone. This does not replace the requirement to complete and fax the BI SAE form.

With receipt of any further information to these events, a follow-up SAE form has to be provided. For follow-up information the same rules and timeline apply as for initial information. All (S)AEs, including those persisting after individual patient's end of trial must be followed up until they have resolved, have been assessed as "chronic" or "stable", or no further information can be obtained.

5.2.6.2.3 Pregnancy

In rare cases, pregnancy might occur in a clinical trial. Once a patient has been enrolled in the clinical trial and has taken trial medication, the investigator must report any drug exposure during pregnancy in a trial participant immediately (within 24 hours) by means of Part A of the Pregnancy Monitoring Form to the sponsor's unique entry point.

The outcome of the pregnancy associated with the drug exposure during pregnancy must be followed up and reported to the sponsor's unique entry point on the Pregnancy Monitoring Form for Clinical Studies (Part B).

The ISF will contain the Pregnancy Monitoring Form for Clinical Studies (Part A and B).

[figure not shown]
As pregnancy itself is not to be reported as an AE, in the absence of an accompanying SAE and/or AESI, only the Pregnancy Monitoring Form for Clinical Studies and not the SAE form is to be completed. If there is an SAE and/or AESI associated with the pregnancy an SAE form must be completed in addition.

5.2.6.2.4 Exemptions to SAE reporting

Not Applicable

5.5 BIOBANKING

Participation in biobanking is voluntary and not a prerequisite for participation in the trial. Biobanking will only occur after a separate biobanking informed consent has been given in accordance with local ethical and regulatory requirements. No samples will be taken for biobanking from patients at sites in China due to regulatory restrictions.

In order to be able to address future scientific questions, patients will be asked to voluntarily donate biospecimens for banking. If the patient agrees, banked samples may be used for future biomarker research and drug development projects, e.g. to identify patients that are more likely to benefit from a treatment or experience an AE, or to gain a mechanistic or genetic understanding of drug effects and thereby better match patients with therapies. Samples will be stored for testing for a period consistent with local regulations.

5.5.1 Methods and timing of sample collection

Detailed instructions on sampling, preparation, processing, shipment and storage are provided in the laboratory manual. For sampling timepoints see [Flow Chart](#). Approximately 48 mL blood will be drawn for DNA, Plasma, and Serum banking.

5.8 APPROPRIATENESS OF MEASUREMENTS

All measurements performed during this trial are standard measurements and will be performed in order to evaluate efficacy and tolerability of BI456906 and to determine pharmacokinetic and pharmacodynamic parameters in an appropriate way. The scheduled measurements will allow monitoring of changes in vital signs, standard laboratory values, and ECG parameters that might occur as a result of administration of study drug. The safety assessments are standard, are accepted for evaluation of safety and tolerability of an s.c. administered drug and are widely used in clinical trials. The pharmacokinetic parameters and measurements outlined are generally used assessments of drug exposure.

6. INVESTIGATIONAL PLAN

6.1 VISIT SCHEDULE

For a detailed overview of the trial procedures and time windows for visits, please refer to the [Flow Chart](#).

The trial consists of a screening visit followed by a 46-week treatment period and a follow-up visit.

The study will last until every randomised patient has completed the last follow-up visit.

After giving his/her Informed Consent, the patient will be screened for inclusion and exclusion criteria for the study at visit 1. Visit 2 will be scheduled after visit 1, after results from central laboratory are obtained, as well as ECG central review. The minimum interval between screening and randomization is 1 week. The patient will be randomized at visit 2 if all inclusion and none of the exclusion criteria are fulfilled.

During the treatment period, there will be a dose escalation period of 20 weeks followed by a dose maintenance period. Total treatment period is 46 weeks.

Windows of ± 1 or ± 2 days is allowed to accommodate scheduling problems. If a delay is observed for a particular visit, the original calendar schedule should be kept for subsequent visits (delays should not accumulate). If a visit is missed the patient should be instructed to reach out to the investigator as soon as possible. Handling of missed drug injections is described in [section 4.1.4](#). Investigator should contact the BI monitor to discuss further schedule.

Follow up visits have to be organized a minimum of 28 days after last drug injection.

Patients with obesity are in general at higher risk for severe illness from COVID-19. In exceptional cases, if standard visits at the trial sites are impossible because of COVID-19 related safety risks, trial conduct may need to be adjusted, strictly consistent with local public health guidance and regulations.

If, in order to minimize the risk of exposure to COVID-19, physical visits should be avoided, the use of remote visits (via phone and/or internet-based means of communication) and local laboratory services for safety and efficacy parameters measurements should be considered if possible. However, study drug shipment to patients might not be possible in all countries to be included. In such situations, picking up trial medication could be done by patient's delegate or by patient at a sterile pharmacy (e.g. "drive-through", "isolated" pharmacy).

Investigators should complete study procedures according to the protocol to the extent possible. The max. number of missing doses of study medication is defined in [section 4.1.4](#). Considering all aspects, the investigator will decide upon each patient's (continued) participation in the planned trials. BI as the sponsor, where required, will support the investigator in their decision finding. It is acknowledged that the investigator may decide to implement protocol deviations where this protects the safety, wellbeing and/or is in the best interest of the patient. All home/remote visits need to be discussed with and approved by the sponsor's trial team. Local regulatory and legal requirements of the participating country still apply

All COVID-19 related deviations from the original schedule of visits and procedures will be documented and the implications considered for the analysis of the trial data.

6.2 DETAILS OF TRIAL PROCEDURES AT SELECTED VISITS

6.2.1 Screening and run-in period(s)

Screening Period

Following informed consent, the patient will undergo visit 1/screening assessments as indicated in the [Flowchart](#). Once the patient has consented, the patient is considered to be enrolled in the trial. The patient should be recorded on the enrolment log and be registered in the IRT.

The assessments must all fall within the acceptable screening visit window but do not need to be performed on the same day.

Re-testing for certain eligibility criteria can be performed once as outlined in [section 3.3](#). The screening phase can be extended up to a maximum of 12 weeks (from visit 1 to visit 2), when needed to allow proper documentation of weight stability. If the patient meets the entry criteria, visit 2 should occur as soon as possible once it has been confirmed that the patient is eligible to continue.

If the patient does not meet the entry criteria, (i.e. fail to meet one or more of the inclusion criteria, and/or meet one or more of the exclusion criteria) following Visit 1 procedures, they should be registered as a screen failure in IRT.

6.2.2 Treatment period(s)

Before visit 2, patients will have to record their food intake in a 3-days food diary (see [section 5.1.5](#)).

Patients who meet all the protocol criteria will be randomized at visit 2. After randomization, patients will start the treatment period which includes a dose escalation phase, followed by the dose maintenance phase as shown in [Figure 3.1: 1](#).

Procedures to be completed at each visit can be found in the Flow Chart.

At visits specified in the Flow Chart, patients should be instructed to come in the fasting state after at least 10 hours without food intake. Water intake is allowed. On days when fasting is required, the clinic visit should ideally be scheduled in the mornings, if this is convenient for the patient.

During visits, vital signs must be measured before blood sampling.
Drug injection should always take place after all assessments of the visit are done.

At each visit, patients should be advised to follow the recommended diet and exercise plan and to record their compliance daily on the provided diary. Diet and exercise counselling sessions are held at visits indicated in the [Flow Chart](#). When necessary from a logistic point of view it is possible to have the diet/exercise counselling on a different day than the actual dosing visit, but within the timewindow of the visit.

Unscheduled visits may be arranged if necessary. Procedures completed during an unscheduled visit will depend on the circumstances under which the visit was scheduled, and at the discretion of the investigator.

Exceptionally, and after consultation with sponsor, one visit could be completed a few days in advance to accommodate for patient's imperatives. The call to IVRS and drug allocation would be made, but the injection would occur as per the initial schedule and allowed time-window.

After completion of the treatment period, patients will have the End of Treatment visit, one week after last drug injection. All patients will then enter the follow-up period and complete the observation period with the follow-up visit which has to be set at least 4 weeks after last drug injection.

If a patient discontinues drug during the treatment period (dose escalation phase, or maintenance phase), the patient will undergo the procedures of "end of treatment" visit, ideally 7 days after the last drug injection.

Safety lab, other laboratory tests during the treatment period (from V3 to visit 17) :

If blood sampling for central lab at the trial site is not possible, safety lab analyses can be performed at a local lab. The results of the lab tests must be transferred to the investigator who ensures medical review and proper documentation in the eCRF.

Minimum required safety lab parameters are

Haematology: Haematocrit, Hemoglobin, Red Blood Cells / Erythrocytes, White blood cells / Leukocytes, Platelet Count / Thrombocytes

Clinical chemistry: ALT (alanine aminotransaminase, SGPT), AST (aspartate aminotransaminase, SGOT), Bilirubin total, Amylase, Lipase

6.2.3 Follow-up period and trial completion

A follow up visit has to be organized after a minimum of 4 weeks after last drug injection as outlined in the [Flow Chart](#) (FC).

Procedures to be completed at the follow-up visit can be found in the Flow Chart. The sequence of visit procedures will be the same as in the treatment period.

If a patient had withdrawn drug prematurely, he should also come for that follow-up visit. In addition, the patient will be asked to return to clinic every 4 weeks to measure body weight until the end of the planned treatment period, i.e. week 46. All efforts should be made at least to conduct the week 46 visit for all patients.

However, if this is not possible, a phone contact should be made at week 46 to obtain vital status and body weight measured at home on the study scale.

7. STATISTICAL METHODS AND DETERMINATION OF SAMPLE SIZE

The primary trial objective includes demonstration of PoCC with respect to a non-flat dose response curve, characterization of the dose-response relationship within the therapeutic range, and selection of the dose range for phase III development. For this purpose, the primary analysis uses methodology for dose finding employing both multiple comparison procedures and modelling techniques (MCPMod).

7.1 NULL AND ALTERNATIVE HYPOTHESES

The null hypothesis is that there is a flat dose response curve across the placebo and the BI 456906 dose groups, with regard to the primary endpoint of percentage change in body weight from baseline to Week 46. The alternative hypothesis is that there is a non-flat dose response curve indicating a benefit of BI 456906 over Placebo.

The MCPMod procedure allows for simultaneous evaluation of different potential dose response patterns, whilst protecting the overall probability of Type I error (one sided 2.5%). The pre-specified models and their parameters used for this test are outlined in [Section 7.2.2](#).

No confirmatory hypothesis testing will be performed in this trial.

7.2 PLANNED ANALYSES

7.2.1 General considerations

Analysis Sets

Statistical analysis will be based on the following analysis sets:

The Full Analysis Set (FAS) is defined as all randomised patients who received at least one dose of study treatment and who have analysable data for at least one efficacy endpoint.

The Treated Set (TS) is defined as all randomised patients who received at least one dose of study treatment.

The Pharmacokinetic Set (PKS) is defined as all patients in the TS who provided at least one BI 456906 concentration which was not excluded due to non-evaluability or an important protocol deviation relevant for PK.

Important Protocol Deviations

Important protocol deviation (IPD) categories will be defined in the IPD specification document. IPDs will be identified no later than in the Report Planning Meeting (RPM).

IPDs may include (but not necessarily be limited to) the following:

- Violation of inclusion or exclusion criteria
- Major deviations from scheduled timing of assessments
- Non-compliance with trial medication

- Treatment dispensing errors
- Use of prohibited or restricted concomitant medication.

Definition of baseline

In general, unless otherwise specified in the TSAP, the last non-missing measurement on or prior to the date of first dose of study treatment will be used as baseline for efficacy and safety variables.

Definition of on-treatment

For the purposes of on-treatment efficacy analyses, the definition of “on-treatment” will be given in the TSAP.

For the purposes of on-treatment safety analyses, an assessment (or AE start date) will be considered “on-treatment” if the assessment date (or AE start date) is between the date of first dose and 28 days after the date of last dose of study treatment.

7.2.2 Primary endpoint analyses

The analysis for PoCC and dose-finding will be performed using multiple comparison and modelling techniques (MCPMod) [R10-1424] whereby several possible dose response models (patterns) will be evaluated, while keeping full control of the type I error at 2.5% (one-sided) to identify the best-fitting model or subset of models.

To account for repeated body weight measurements over time and for inclusion of baseline covariates in the model, a mixed model for repeated measures (MMRM) analysis will first be carried out. The MMRM will include fixed effects for baseline body weight and baseline by visit interaction as continuous covariates, and treatment, gender, visit and treatment-by-visit interaction as factors. Unstructured covariance will be used to model the relationship between pairs of endpoint measurements taken at different visits on the same patient. The Kenward-Roger approximation will be used to estimate the denominator degrees of freedom. The TSAP will specify approaches to be taken to resolve possible non-convergence issues, including if necessary, the selection of a simpler covariance structure.

Covariate-adjusted fixed effect estimates of mean percentage change in body weight at Week 46 for each treatment group and the covariance matrix will be extracted from the MMRM fit. These will be used for the subsequent MCPMod analysis.

For the PoCC testing and for the sample size calculation, the basic shape of each of the models to be tested must be pre-defined. The following model assumptions and resulting graphs (Figure 7.2.2: 1) have been selected to cover a plausible and diverse range of monotone dose response patterns, with placebo mean response assumed to be zero and the mean response at the highest BI 456906 dose assumed to be -10.0 (i.e. a percentage reduction from baseline in body weight of 10%):

- Linear
- Exponential: 50% of maximum effect achieved at dose 3.6 mg
- Emax1: 90% of maximum effect achieved at dose 4.8 mg

- Emax1: 70% of maximum effect achieved at dose 4.8 mg
- Sigmoid Emax: 50% of maximum effect achieved at dose 2.4 mg; 90% of max effect achieved at dose 4.8 mg

[figure not shown]

Figure 7.2.2: 1 Dose response patterns considered for the MCPMod analysis.

PoCC will be established if at least one model is statistically significant, rejecting the null hypothesis of a flat dose response relationship for percentage change in body weight jointly over the candidate dose response models, with a contrast test controlled for the family-wise type I error rate at one sided $\alpha = 2.5\%$.

If PoCC is established, the statistically significant (best fitting) model(s) from the above candidate set will be refitted to the data to generate new estimates for all model parameters from the data. The target dose(s) will be estimated from the best fitting model(s) by incorporating information on the minimum clinically relevant effect and accounting for safety.

The primary analysis of percentage change from baseline in body weight at Week 46 will be performed using the FAS and will assign patients to the randomised maintenance dose. It will include all available data without regard to whether patients started the maintenance period

with a lower dose than the one randomised to. For patients who discontinued treatment early, a distinction will be made according to whether this is due to a COVID-19 pandemic-related reason or not. Patients who discontinued treatment early due to a pandemic-related reason (e.g. direct COVID-19 infection, drug supply issue, site closure, quarantine preventing site access) will have data handled after discontinuation as if they were missing. Patients who discontinued treatment early for any other reason will have all available data included after discontinuation, irrespective of whether such patients subsequently received any permitted anti-obesity treatments.

The above approach to the primary analysis specifies a hypothetical strategy for the intercurrent event of pandemic-related early treatment discontinuation, and a treatment policy strategy for the intercurrent event of non-pandemic-related early treatment discontinuation.

The primary endpoint will be summarised descriptively overall, and by pre-specified subgroups (to be specified in the TSAP, but which may include e.g. subgroups based on gender, baseline BMI and age at screening).

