7.5 DETERMINATION OF SAMPLE SIZE

Sample size evaluation was performed using simulation in R software (version 3.6.1), with 10000 simulations performed for each scenario summarised below.

The sample size calculation was based on the following assumptions:

- An overall significance level of 2.5% (one-sided) for the contrast test of the null hypothesis of flat dose response
- The (monotone) dose response shapes specified in [Section 7.2.2](#)
- A placebo effect size (mean percentage change from baseline in body weight at Week 46) of zero
- A maximum effect size (mean percentage change from baseline in body weight at Week 46) in the highest dose group of -10.0%
- A standard deviation of 7.0% [[R20-0479](#)].

Simulations were also performed to investigate departures from the assumed true maximum effect stated above, as well as for different scenarios for the true nature of the dose response relationship. The probability of success for each of these scenarios is summarised in [Table 7.5: 1](#) below.

A success was defined as meeting all 3 of the following criteria:

1. Null hypothesis of flat dose response was rejected in favour of at least one of the alternative candidate models, and
2. A target dose was selected within the dose range using the following criterion: difference in mean between selected dose and placebo < -9.0%, and
3. Proportion of patients in the highest dose group meeting the responder definition (percentage change in body weight from baseline < -10.0%) was greater than 35%.

Table 7.5: 1 Probability of success with N=70 patients in each treatment group and SD = 7.0%.

| | Probability of success (%) | | | | | | |
|-------------------------|----------------------------|-------------|-------------|--------------------|--------------------|---------------------|-------------|
| | | Linear | Exponential | E _{max} 1 | E _{max} 2 | SigE _{max} | AVERAGE |
| True maximum effect (%) | -9.0 | 48.9 | 48.9 | 48.8 | 49.0 | 65.3 | 52.2 |
| | -9.5 | 67.8 | 68.3 | 69.1 | 67.9 | 79.2 | 70.5 |
| | -10.0 | 82.8 | 83.3 | 83.8 | 83.3 | 89.0 | 84.4 |
| | -10.5 | 92.4 | 92.6 | 93.2 | 92.2 | 95.6 | 93.2 |
| | -11.0 | 97.1 | 97.3 | 97.8 | 96.5 | 98.4 | 97.4 |

A sample size of 70 patients per treatment group gives a probability of success of greater than 80% for all assumed dose response shapes, with the assumed maximum dose effect and standard deviation as stated earlier.

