Once the significance of a dose response signal is established, the dose response profile and the target dose will be estimated from the best-fitting dose response model, defined as the model with the smallest Akaike Information Criterion (AIC). The target dose for MCPMod purposes is defined as the smallest BI 456906 dose which is estimated to achieve a mean reduction in body weight of 9% more than the mean reduction obtained with placebo. If no dose within the range studied by the trial meets this criterion, then it will be concluded that MCPMod has not identified a target dose.

Estimates for each dose group will be calculated and will be based on the final dose-response model. In practice, the choice of the target dose to be investigated in Phase 3 will be based upon efficacy as well as considering tolerability and safety and other relevant information.

The results of the MCPMod analysis will be displayed in the following ways:

- A summary table will be produced containing:
 - The adjusted means from the MMRM for each dose group at Week 46 and their estimated variance
 - The updated contrast coefficients for each dose group and for each of the candidate dose response models specified above
 - The test statistics, adjusted p-values and critical values for each candidate dose response model.
- Another summary table will be produced containing:
 - The adjusted means from the MMRM for each dose group and the adjusted mean differences from placebo at Week 46
 - Predicted means for each dose group and mean differences from placebo using each of the dose response model types fitted to the data (Linear, Exponential, Emax and Sigmoid Emax)
- For each model shape, the predicted dose response curve and the 95% CI for the predicted shape will be plotted and overlaid with the adjusted means from the MMRM and their 95% CIs for each dose group at Week 46.
- For each model shape, the placebo-corrected dose response curve will be plotted and overlaid with the adjusted mean differences from placebo from the MMRM and their 95% CIs for each dose group at Week 46.

The predicted BI 456906 dose which achieved a 9% mean reduction compared with placebo will be tabulated for the significant model shapes (Linear, Exponential, Emax and Sigmoid Emax).

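### The SAP takes the dose-response curve and target dose from one AIC-selected model: the curve's 95% CI ignores the selection, and the visible text gives the target dose no interval

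*Protocol*

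**What the plan says.** Protocol 7.2.2 leaves open whether one model or several are used: "The target dose(s) will be estimated from the best fitting model(s) by incorporating information on the minimum clinically relevant effect". SAP 7.4.1 (MCPMod part) closes this. Once a dose-response signal is established, "the dose response profile and the target dose will be estimated from the best-fitting dose response model", and best-fitting means smallest AIC. The dose-group estimates are also based on that final model. The target dose is the smallest dose estimated to give a mean reduction 9 points greater than placebo.

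SAP 7.4.1 plans these displays of precision:

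- For each model shape, "the predicted dose response curve and the 95% CI for the predicted shape will be plotted", overlaid with the MMRM adjusted means and their CIs.
- For each shape, a placebo-corrected curve, overlaid with the MMRM differences from placebo and their 95% CIs. No model-based CI is mentioned for this plot.
- "The predicted BI 456906 dose which achieved a 9% mean reduction compared with placebo will be tabulated for the significant model shapes". No interval is mentioned.
- Separately, an MMRM table with the difference from placebo and its 95% CI for each dose.

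The visible text contains no bootstrap, model averaging or other allowance for model selection.

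**The concern.** Four model types, with two to four parameters, are fitted to five dose-group means, and the data choose among them. A CI computed as if the chosen shape had been known in advance leaves out one source of error. If AIC picks a simpler model than the truth, the curve is displaced and its CI is too narrow to show it.

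Separately, the target dose is found by inverting the fitted curve at 9%. Where the curve is flat near that level, a small vertical error becomes a large horizontal one. Choosing doses for phase III is a stated purpose of the trial (protocol sections 2 and 7). A target dose reported as a single number, beside a curve with optimistic bands, would look better determined than 70 patients per arm can make it.

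**Working it through.** **Inputs.** Protocol 7.5: "An overall significance level of 2.5% (one-sided) for the contrast test of the null hypothesis of flat dose response"; "A standard deviation of 7.0" percentage points; 70 per arm in five arms; placebo mean 0; mean at 4.8 mg -10%. Shapes come from protocol 7.2.2 and SAP 7.4.1. The selection rule and the 9% criterion come from SAP 7.4.1.

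**Shapes.**
- Emax1: ED50 = 4.8 x 0.1/0.9 = 0.533 mg.
- Emax2: ED50 = 4.8 x 0.3/0.7 = 2.057 mg.
- Sigmoid: ED50 = 2.4 mg, Hill h with 2^h = 9, so h = 3.170.
- Exponential: delta = 1.969.

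Scaled to -10 at 4.8 mg, the sigmoid means at 0, 0.6, 2.4, 3.6 and 4.8 mg are 0, -0.14, -5.56, -8.70 and -10.

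**The plan's own figures first.** The contrast coefficients in SAP Table 7.4.1:1 reproduce to three decimals. Protocol 7.5 states: "A sample size of 70 patients per treatment group gives a probability of success of greater than 80% for all assumed dose response shapes". Simulating its three success criteria with AIC selection (10,000 trials per cell; critical value 2.25 on 345 df) gives, at -10%, 82.7 / 82.1 / 83.9 / 84.2 / 89.3-89.9 against the printed 82.8 / 83.3 / 83.8 / 83.3 / 89.0. All 25 cells of Table 7.5:1 agree within about 1.2 points.

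**Coverage of the planned CI for the predicted mean.** This is the nominal 95% CI of the AIC-selected model. The SAP does not name the CI method, so the delta method is assumed; the fitting bounds are also an assumption. The run used 4,000 trials per shape:

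| True shape | True family chosen | 0 mg | 0.6 mg | 2.4 mg | 3.6 mg | 4.8 mg |
|---|---|---|---|---|---|---|
| Linear | 79% | 92.9 | 93.6 | 90.6 | 93.2 | 92.8 |
| Exponential | 87% | 92.1 | 94.3 | 91.0 | 92.5 | 93.3 |
| Emax1 | 95% | 95.0 | 94.2 | 95.6 | 95.6 | 95.8 |
| Emax2 | 83% | 91.4 | 92.7 | 88.1 | 93.8 | 91.6 |
| Sigmoid | 48% | 91.1 | 76.8 | 87.3 | 80.7 | 89.2 |

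Repeat runs differ by up to about two points. The rounded figures used in the verdict are 89-95% for the first four shapes and, under the sigmoid, 75% at 0.6 mg, 81% at 3.6 mg and 88-92% elsewhere.

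**Why the sigmoid case fails, by hand.** The least-squares line through the five sigmoid means has slope -2.302 and intercept 0.370. Its sum of squared errors is 2.145. Each arm mean has variance 49/70 = 0.7, so the lack of fit is 2.145/0.7 = 3.06. The two extra sigmoid parameters would improve the fit by about 3.06 + 2 = 5 on average, against an AIC penalty of 4. The choice is therefore close, and simulation has AIC choosing linear in 44% of trials.

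The line's error is -0.88 at 0.6 mg and +0.79 at 3.6 mg, with standard errors 0.51 and 0.46, which is about 1.7 standard errors in both places. At the other doses it is 0.6 to 1.1 standard errors. The coverage losses follow this pattern. At 4.8 mg the line gives a placebo-corrected effect of 4.8 x (-2.302) = -11.05, an excess of 1.05. Multiplied by 0.44 this is about 0.46, close to the simulated bias of -0.51.

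**Target dose.** True values solve mean difference = -9; for example linear 4.8 x 0.9 = 4.32 mg, and Emax1 0.81 x 0.533/0.19 = 2.27 mg.

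| True shape | True target (mg) | 95% sampling range when found (mg) |
|---|---|---|
| Linear | 4.32 | 3.3-4.8 |
| Exponential | 4.61 | 4.1-4.8 |
| Emax1 | 2.27 | 0.7-4.4 |
| Emax2 | 3.50 | 1.8-4.7 |
| Sigmoid | 3.79 | 2.7-4.6 |

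No target is found in 11-18% of trials. A rough check: the 4.8 mg effect has a sampling SD of about 1.05, so P(effect short of 9) = Phi(-1/1.05) = 17%.

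**Repeating the selection.** A parametric bootstrap that reselects by AIC in each draw covers about 91-98% for the curve and 94-97% for the target dose. Its 95% target-dose interval has no upper limit within 4.8 mg in 73-89% of trials in this run. The rough check is Phi(1.96 - 1/1.05) = 84%.

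**The case against.** The strongest reply is that the plan does not depend on the selected model alone. MMRM differences from placebo with 95% CIs are planned for every dose and owe nothing to AIC. In simulation they cover 94-96%, with width 2 x 1.96 x 7 x sqrt(2/70) = 4.64. The 9% dose is tabulated for every significant shape, predictions are given under all four model types, and SAP 7.4.1 says the phase 3 dose also rests on tolerability, safety and other information. All of this stands. What it does not supply is an interval for an interpolated target dose. A spread across shapes is not sampling error.

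Four stronger readings are tempting, and the documents do not support them.

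- **That the trial's dose effects in general have invalid error bars.** Only the model-based estimates are affected.
- **That coverage falls to 23% at 0.6 mg.** That figure arises for a model-based CI of the placebo-corrected effect, which the SAP does not plan. It is also partly a delta-method artefact: with the true family fitted, coverage there is only 69%.
- **That Table 7.5:1 shows false target doses.** Its first row, "9.0 | 48.9 | 48.9 | 48.8 | 49.0 | 65.3 | 52.2", gives the probability of meeting three criteria jointly. At a true -9.0% the top dose sits exactly on the threshold and meets the SAP's definition, so naming it is not an error. The higher sigmoid figure fits the selection bias above but is not an error rate.
- **That the wide target-dose ranges are caused by selection.** Under Emax1, AIC finds the right family in 95% of trials and the CIs are nominal, yet the range is widest there. That is sampling error.

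SAP 7.4.2 is not in the text supplied. It is cited elsewhere for a missing-data sensitivity analysis, but a supplementary interval there cannot be ruled out.

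**Conclusion.** The point holds, within limits. The planned 95% CI for the selected curve is mildly optimistic for most shapes (about 89-95%) and materially so if the truth is sigmoid (about 75% at 0.6 mg, 81% at 3.6 mg, 88-92% elsewhere). At 4.8 mg under the sigmoid shape the shortfall comes mainly from a bias of about 0.5 points rather than from interval width. The more consequential gap is the target dose, whose sampling range can span most of the studied doses and which the visible text reports without an interval.

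The anchor is SAP 7.4.1; the protocol sentence alone would allow several models. The type I error of the contrast test, the sample size and the MMRM comparisons are not affected. The sizes assume SD 7%, 70 evaluable per arm, a top effect of -10%, delta-method CIs and the stated fitting bounds.

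**What to change.** In SAP 7.4.1, keep the AIC-best model for the point estimates and add a parametric bootstrap:

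1. Draw at least 1000 vectors from the multivariate normal given by the Week 46 MMRM adjusted means and their covariance matrix.
2. In each draw, refit all candidate models and repeat the AIC selection.
3. Report percentile 95% CIs for the final model's predicted means, its placebo-corrected effects and the target dose. Count draws with no qualifying dose as above 4.8 mg, and report the percentage of such draws.
4. Use these intervals in place of the model-conditional CI for the final model.

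The work is a SAP paragraph and a short R step on estimates already extracted for MCPMod. The cost is in what will be shown. Intervals become wider, and under the design assumptions the target-dose interval will have no upper limit within 4.8 mg in roughly 75-90% of trials. The change corrects the error bars; it does not remove the bias of about 0.5 points at 4.8 mg under the sigmoid shape, because the point estimate still comes from the selected model.
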